12.5 Documentation and Reporting of SAEs

Every SAE will always be documented in the patient file and in the eCRF even if they are

- not severe
- meeting CTCAE grade 1 or 2
- not at least possibly related
- declared in the protocol as being exempt from reporting without undue delay, by the investigator to sponsor (refer to Section 12.5.1)
- primarily attributed to the underlying disease

Every SAE has to be reported immediately to the Sponsor Delegated Person/ Coordinating Investigator and SZB except those SAEs the protocol identifies as not requiring immediate reporting. However, **every SAE that is considered related to the IMP will always be reported to the Sponsor Delegated Person/ Coordinating Investigator without undue delay** According to the documentation of AEs any adverse event in patients of

the control arm meeting the criteria of an SAE will also be recorded although no study drug will be administered to ensure comparability of the safety data of the two study arms.

The documentation of the SAEs for a patient is carried out as described under 12.4, the reporting of SAEs for study patients is carried out within the following time periods:

- after the subject has been randomized and has received IMP for the first time
- up to 24h after the subject has received the last dose of IMP
- after these time periods until end of trial, when the SAE is believed to be related to the IMP
- after the end of trial when the investigator becomes aware of a SAE with a suspected causal relationship to the IMP

Any SAE occurred after application of study drug should be reported **immediately** after investigator awareness of the event to the sponsor (at the latest within 24 hours):

Study Coordinating Center of the SZB
Studienzentrale Studienzentrums Bonn (SZB)
[contact]
E-Mail: [contact]

Reporting should occur by fax on the **SAE report form** provided for this purpose. Symptoms, signs and laboratory changes should, as far as possible, be combined into one **single diagnosis**. The investigator is responsible for assessing the event (seriousness, intensity, causality). If necessary information is not fully available at this time, follow-up reports should be sent as soon as possible. Questions must be answered promptly. Further information and details how to report are described in the **Safety Management Plan**.

12.5.1 Serious Adverse Events exempted from expedited reporting

According to the ICH Guideline E19² in certain situations selective safety reporting may be appropriate. This applies for example if the IMP has received a marketing authorization from a regulatory authority, the safety profile is well-known, the clinical pharmacology has been described and understood, post-authorization data is sufficiently available.

In this clinical trial the test-IMP has a marketing authorization for more than 30 years in Germany and a very well-know safety profile from a large number of post-authorization data [54]. The aim of this trial is to provide evidence of efficacy of nicotine treatment in patients suffering from DGE after PD.

Surgical resection is a pre-planned procedure and not considered as trial treatment. Therefore, complications from surgical resection (PD) from the date of surgery until the end of follow-up are not considered AEs/SAEs unless the complications are considered to be related to treatment with the IMP. Surgical complications will be documented in the eCRF and the patient file.

Furthermore, events that are probably related to the underlying disease are not considered as AE/SAE as long as the severity of the event is to be expected and not aggravated.

² ICH Guideline E19 on a selective approach to safety data collection in specific late-stage pre-approval or post-approval clinical trials (16-Mar-2023)

The underlying disease is a condition prior to inclusion in the clinical trial. Events that are probably related to the underlying disease are not considered as AE/SAE as long as the event and the severity of the event are to be expected and not aggravated.

The following events are most likely to occur after surgical resection or are most likely related to the underlying disease:

- Postoperative pancreatic fistula
- Relaparotomy
- Postoperative haemorrhage
- Insufficiency of the biliodigestive anastomosis
- Insufficiency of the GE (Gastroenterostomy)
- (Superficial) wound infections
- Intra-abdominal abscess
- Pleural effusion
- Pneumonia

In recent studies, nicotine application was extremely safe in terms of anastomotic healing and surgical site infections [59,60]

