Attachment 001 to SOP MW-009.001

Version 001

Page 15 of 69

Clinical Trial Protocol version 2.0 of 28-JUN-2023

Effective Date: 18-Mai-2022

	Screening Visit	Treatment Phase		Follow up Phase		End of Trial
Time points (accepted deviation)	Day -28 to Day -1	Day 1 (Surgery)	Day 2 to Day 7	Day 14 (+/- 1 Day)	Day 21 (+/-1 Day) or Discharge	Day 30 (+/- 2 Days)
Visit No.	0	1	1.2 to 1.7	2	3	4
QLQ-C30						√
PAN26						√

¹ according to the definition of the International Study Group of Pancreatic Surgery. NGT requirement + solid food intake on every visit day indicated, all other parameters only on Visit 1.3, 1.7, 2 and 3.

² especially: surgical site infections, cardiovascular events, mortality

³ Visit 1 only Lymphadenectomy, re-intervention, re-operation, nausea, cardiovascular events. Visit 1.2, 1.3, 1.5-1.7 no assessment. Visit 1.4, 2, 3, 4 only pancreatic fistula, postoperative hemorrhage, intra-abdominal fluid collections, re-laparotomy

⁴ Exclusion Criterion No. 5 can only be answered during surgery

3 Abbreviations

AR	Adverse (Drug) Reaction
AE	Adverse Event
AMG	Arzneimittelgesetz
CA	Competent Authority
CI	Coordinating Investigator
CRA	Clinical Research Associate
CRF	Case Report Form
CRO	Contract Research Organization
CTR	Clinical Trial Regulation
DGE	Delayed Gastric Emptying
EC	Ethics Committee
FPFV	First Patient First Visit
FPI	First Patient In
GCP	Good Clinical Practice
GDPR	General Data Protection Regulation
ICH	International Conference on Harmonization
IMP	Investigational Medicinal Product
ISF	Trial site File
LPLV	Last Patient Last Visit
LPO	Last Patient Out
NGT	Naso-gastric tube
PD	Pancreatoduodenectomy
PI	Principal Investigator
SAR	Serious Adverse Reaction
SAE	Serious Adverse Event
SDP	Sponsor Delegated Person
SUSAR	Suspected Unexpected Serious Adverse Reaction
SZB	Study Center Bonn (Studienzentrum Bonn)
UAR	Unexpected Adverse Reaction

4 Trial Administration structure

Coordinating Investigator and Sponsor Delegated Person	[name] Department of Surgery University Hospital Bonn [name] [contact] Email: [contact]
Sponsor	Medical Faculty of the University of Bonn, represented by the Dean [name]
Coordinating institution	Clinical Study Core Unit, Study Center Bonn (SZB) Institute for clinical chemistry and clinical pharmacology University Hospital Bonn [name]
Participating trial site(s)	6 German sites are planned

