12.2.3 Assessment of Causality

Determination of the relationship of the adverse events to the medicinal product(s) being studied after having evaluated all accessible data according to the following classification:

Suspected relationship (related):

The temporal relationship between the event and the administration of the IMP makes a **causal relationship possible, probable, or definite**, or other drugs, therapeutic interventions or underlying conditions do not provide a sufficient explanation for the observed event.

No suspected relationship (not related):

The temporal relationship between the event and the administration of the IMP makes a **causal relationship unlikely or impossible (i.e. not related)**, or other drugs, therapeutic interventions or underlying conditions provide a sufficient explanation for the observed event.

The evaluation should consider nature and pattern of the reaction, temporal relationship to study medication, the clinical status of the patient, the concomitant medication and other relevant parameters. When the final causality assessment is unknown and it is uncertain whether or not the investigational product caused the event, then the event should be handled as an SAE related (suspected) to the investigational product for reporting purposes. If the investigator believes that the SAE is not related to the investigational product but is potentially related to the conditions of the trial the relationship should be specified in the narrative section of the SAE report form.

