12.5.2 Reporting of events to authorities and ethics committees

AEs

The sponsor shall submit the documentation of AEs to the responsible competent authority upon request.

SUSARs

Regarding suspected unexpected serious adverse reactions (SUSARs) the sponsor has to inform the responsible ethics committee, the competent higher federal authority and the investigators participating in the clinical trial. The sponsor shall report electronically and without delay to the European Medicines Agency (EMA) via database Eudravigilance all relevant information about SUSARs to IMPs occurring in that clinical trial or occurring in any of the subjects of the clinical trial, and which are identified by or come to the attention of the sponsor after the end of the clinical trial.

The period for the reporting of SUSARs by the sponsor shall take account of the seriousness of the reaction:

- in the case of fatal or life-threatening SUSARs, as soon as possible and in any event not later than seven calendar days after the sponsor became aware of the reaction, followed by as complete a report as possible within 8 additional calendar days;
- in the case of non-fatal or non-lifethreatening SUSARs, not later than 15 calendar days after the sponsor became aware of the reaction.

Re-examination of the risk-benefit assessment

The sponsor shall rapidly inform the competent authority (CA) of any information that might materially influence the benefit-risk assessment of a medicinal product or that would be sufficient to consider changes in medicinal

product administration or in the overall conduct of a clinical investigation represents such situations. This includes in particular:

- For an "expected," serious ADR, an increase in the rate of occurrence which is judged to be clinically important.
- A significant hazard to the patient population, such as lack of efficacy with a medicinal product used in treating life-threatening disease.
- A major safety finding from a newly completed animal study (such as carcinogenicity).

Annual Safety Report (ASR)

Regarding investigational medicinal products other than placebo, the sponsor shall submit annually to the competent authority (CA) a report on the safety of each investigational medicinal product used in the clinical trial. The safety report is prepared in accordance with the ICH Guideline E2F "Development Safety Update Report - DSUR".

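### Section 12.5.1 takes resection complications and expected disease-related events out of the AE/SAE definition, although its heading and Section 12.5 exempt them only from prompt reporting

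*Protocol*

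**What the plan says.** All references are to the protocol.

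- **12.5.1, surgical complications.** From surgery to the end of follow-up, complications of the resection "are not considered AEs/SAEs unless the complications are considered to be related to treatment with the IMP". The same paragraph adds: "Surgical complications will be documented in the eCRF and the patient file".
- **12.5.1, underlying disease.** A second carve-out, which appears twice in slightly different words, begins "events that are probably related to the underlying disease are not considered as AE/SAE as long as the severity of the event". The condition that follows is an expected severity without aggravation. Nine event types are then listed as most likely surgical or disease-related.
- **12.5.** Every SAE is always documented in the patient file and eCRF. This expressly includes SAEs that are not at least possibly related, those "primarily attributed to the underlying disease", and those "declared in the protocol as being exempt from reporting without undue delay, by the investigator to sponsor", with a cross-reference to 12.5.1.
- **12.2.3.** An event is not related if "other drugs, therapeutic interventions or underlying conditions provide a sufficient explanation for the observed event".
- **Section 2, footnote 2 to the AE/SAE row.** AEs and SAEs are collected "especially: surgical site infections, cardiovascular events, mortality".
- **14.2.2 and 14.2.5.** Adverse events and serious adverse events are a secondary endpoint. Safety parameters are summarised by treatment.

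**The concern.** Section 12.5 and the body of 12.5.1 cannot both be followed. A site that follows 12.5 enters an anastomotic leak that prolongs the hospital stay as an SAE and only skips the prompt report. A site that follows 12.5.1 enters no AE at all, unless the investigator attributes the leak to the patch. If sites choose differently, AE and SAE counts will differ by site for reasons unrelated to the patients.

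If all sites follow 12.5.1, entry to the AE/SAE data depends on an attribution opinion. Under 12.2.3 the operation itself is a sufficient reason to call an event unrelated, and after pancreatoduodenectomy it will usually be available as an explanation. The investigator is blinded (10.12). An excess of complications under nicotine could therefore not be recognised case by case. It would show as a difference in rates between arms, which needs all events to be counted.

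**Working it through.** No figure in the protocol is at stake, so there is nothing to reproduce. The check is a comparison of sections, followed by an illustration.

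**1. Are these events AEs/SAEs?**

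| Section | Answer |
|---|---|
| 12.1.1 | Yes; an AE needs no causal link to the product |
| 12.1.4 | Yes; complications in hospital count as AEs, and as serious if they prolong the stay |
| 12.4 | Opens with a narrower rule (AEs relevant to the evaluation), then asks for all AEs from first dose to discharge in the CRF |
| 12.5 | Yes; an event exempted under 12.5.1 is still a documented SAE |
| 12.5.1 heading | Yes; exempt from expedited reporting only |
| 12.5.1 text, surgical | No, unless considered IMP-related |
| 12.5.1 text, disease | No, while expected and not aggravated |
| Schedule footnote 2 | Yes for surgical site infections, which belong to the AE/SAE row |

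The text of 12.5.1 stands alone against the rest, including its own heading.

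**2. Which of the nine listed events have another scheduled capture?**

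- Pancreatic fistula, haemorrhage and relaparotomy have checks in 11.1.7 and footnote 3.
- Intra-abdominal abscess is partly covered by the check for fluid collections and is an item in the DGE grading table (11.1.6).
- Wound infection has no check in 11.1.7. Surgical site infection is a named secondary endpoint, and its only scheduled route is the AE/SAE row through footnote 2. Section 12.5.1 closes that route for infections not attributed to the patch.
- Pneumonia, pleural effusion, biliodigestive insufficiency and gastroenterostomy insufficiency have no check in 11.1.7.

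So 9 − 4 = 5 listed event types lack a dedicated check.

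**3. Illustration of the dilution.** The event rates and the share f of events judged IMP-related are assumptions; n = 120 per arm is from 9.6. Filtering both arms equally turns p0 and p1 into f·p0 and f·p1. Approximate power, two-sided alpha 0.10:

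power = Φ[(|p1 − p0| − 1.645·SE0)/SE1], where SE0 = √[p̄(1 − p̄)·2/n] and SE1 = √{[p0(1 − p0) + p1(1 − p1)]/n}.

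| Share kept (f) | Expected events, 10% vs 20% | Power | Expected events, 20% vs 35% | Power |
|---|---|---|---|---|
| all | 12 vs 24 | 70% | 24 vs 42 | 83% |
| 50% | 6 vs 12 | 43% | 12 vs 21 | 52% |
| 25% | 3 vs 6 | 27% | 6 vs 10.5 | 31% |
| 10% | 1.2 vs 2.4 | 16% | 2.4 vs 4.2 | 17% |
| 5% | 0.6 vs 1.2 | 12% | 1.2 vs 2.1 | 13% |

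The ratio between arms survives the filter, but the counts that would show it do not. The protocol plans no such test, and the approximation is rough at the smallest counts. The expected counts are the more useful columns.

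**The case against.** The strongest reply is that the trial does not depend on the AE form for its safety comparison. Fistula, haemorrhage, fluid collections, re-intervention, re-operation, Clavien-Dindo grade, mortality and cardiovascular events are secondary endpoints in their own right. They are summarised by arm with no causality filter, and surgical complications still enter the eCRF. This stands and sets the size of the point. It does not resolve the contradiction or restore the AE/SAE endpoint. Clavien-Dindo may catch part of the five unchecked event types, but 11.1.7 has no check for it either.

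Several stronger readings are tempting, and the documents do not support them:

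- *All nine listed events are lost.* They leave the AE/SAE data, but surgical complications remain documented and four of the nine have other scheduled capture.
- *Deaths after a surgical complication go uncounted.* Mortality is a separate endpoint and part of MTL30 at Day 30.
- *Disease-related events count only if the patch is blamed.* Their test is different: expected and not aggravated. It is still an attribution judgement.
- *The sponsor cannot meet its duty in 12.5.2 to report "an increase in the rate of occurrence which is judged to be clinically important".* That item concerns expected serious adverse drug reactions, which already presuppose suspected causality. The effect on it is at most indirect.
- *The DSMB cannot see these events.* Section 13 speaks of safety data in both arms and lets the DSMB be asked to review any trial data. Its charter is not shown.
- *Most patients fall outside the label that justifies the exemption.* In the retrospective cohort in 14.2.3, 186/274 = 68% were non-smokers, or about 163 of 240 if that mix recurs. This does not measure lost events, and 12.5.1 also argues that surgery is not trial treatment.
- *The safety comparison is biased in a known direction.* With a blinded judge, the expected effect is loss of events and dilution.

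**Conclusion.** The contradiction is certain from the text alone. Section 12.5.1 redefines as non-AEs the events that its heading and 12.5 exempt only from prompt reporting, and it conflicts with 12.1.1, 12.1.4, the collection rule in 12.4 and schedule footnote 2.

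The consequence is moderate. The AE/SAE endpoint by arm would be filtered by attribution, and five of the nine listed event types would have no dedicated check, one of them (surgical site infection) a named secondary endpoint. Most of the major complications remain comparable through their own endpoints. How many events would be lost cannot be derived from the protocol, because it depends on how often investigators attribute a complication to the patch.

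**What to change.** Bring 12.5.1 into line with its heading and with 12.5:

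1. Delete the words that remove events from the AE/SAE definition, in the surgical carve-out and in both statements of the disease-related one.
2. State that resection complications and disease-related events are recorded in the eCRF as AEs/SAEs, with date, intensity, seriousness and causality, whatever their attribution.
3. Exempt all such events not considered IMP-related from the 24-hour report only. The exemption should not be tied to the nine listed types. If it were, an unlisted serious resection complication within the reporting window of 12.5 would become reportable within 24 hours.
4. Tabulate these events by arm in the AE/SAE tables and in the data given to the DSMB. This also keeps open the route for surgical site infections in footnote 2.

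The cost is a wording change and more AE form entries per patient, for events that sites mostly have to document already. With the exemption worded this broadly, no expedited reports are added.

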12.5.2 Reporting of events to authorities and ethics committees

AEs

The sponsor shall submit the documentation of AEs to the responsible competent authority upon request.

SUSARs

Regarding suspected unexpected serious adverse reactions (SUSARs) the sponsor has to inform the responsible ethics committee, the competent higher federal authority and the investigators participating in the clinical trial. The sponsor shall report electronically and without delay to the European Medicines Agency (EMA) via database Eudravigilance all relevant information about SUSARs to IMPs occurring in that clinical trial or occurring in any of the subjects of the clinical trial, and which are identified by or come to the attention of the sponsor after the end of the clinical trial.

The period for the reporting of SUSARs by the sponsor shall take account of the seriousness of the reaction:

- in the case of fatal or life-threatening SUSARs, as soon as possible and in any event not later than seven calendar days after the sponsor became aware of the reaction, followed by as complete a report as possible within 8 additional calendar days;
- in the case of non-fatal or non-lifethreatening SUSARs, not later than 15 calendar days after the sponsor became aware of the reaction.

Re-examination of the risk-benefit assessment

The sponsor shall rapidly inform the competent authority (CA) of any information that might materially influence the benefit-risk assessment of a medicinal product or that would be sufficient to consider changes in medicinal

product administration or in the overall conduct of a clinical investigation represents such situations. This includes in particular:

- For an "expected," serious ADR, an increase in the rate of occurrence which is judged to be clinically important.
- A significant hazard to the patient population, such as lack of efficacy with a medicinal product used in treating life-threatening disease.
- A major safety finding from a newly completed animal study (such as carcinogenicity).

Annual Safety Report (ASR)

Regarding investigational medicinal products other than placebo, the sponsor shall submit annually to the competent authority (CA) a report on the safety of each investigational medicinal product used in the clinical trial. The safety report is prepared in accordance with the ICH Guideline E2F "Development Safety Update Report - DSUR".

The data-lock point of the patient data included and analyzed in the report refers to the date of approval of the clinical trial by the competent authority. The sponsor will provide the report within 60 days of the data-lock point annually.

Arrangements to protect trial participants against imminent danger

Whenever the safety of subjects is compromised and the sponsor and investigator are taking measures to protect subjects from imminent danger, the sponsor has to inform the competent authority of such arrangements and their underlying circumstances, as soon as possible.

12.6 Pregnancy

Any pregnancy that occurs during trial participation must be reported to the Sponsor. To ensure subject safety, each pregnancy and pregnancy outcome must be reported to the Sponsor Delegated Person/Coordinating Investigator and the SZB. For this purpose, the investigator documents and reports the pregnancy and outcome on the registration forms provided for this purpose and remits this immediately (at the latest after 24 hours) to the Sponsor Delegated Person/Coordinating Investigator and the SZB.

The pregnant subject has to discontinue the treatment with the IMP permanently and has to be excluded from the trial.

The pregnancy itself is not classified as an AE or an SAE, but must be followed up to determine outcome (including premature termination) and status of mother and child. According to CTR, pregnancies shall be subject to the same obligation to report as adverse reactions. The investigator will request this information after the scheduled date of birth and provide it in writing to the (sponsor/sponsor's representative).

Pregnancy complications and elective terminations for medical reasons must be reported as an AE or SAE.

Any SAE occurring in association with a pregnancy brought to the investigator's attention after the subject has completed the trial and considered by the investigator as possibly related to the study treatment, must be reported.

If the outcome of the pregnancy corresponds to one of the following cases

- spontaneous or therapeutic abortion or voluntary abortion

- stillbirth
- the presence of birth defects, or
- congenital anomalies (also in miscarriages, stillbirths or premature death),

the investigator reports this case as SAE. In the case of stillbirth, the (presumed) causality is documented. Reporting should occur by fax on the **SAE report form** provided for this purpose..

